4.2.2.2 Supplementary analyses

There will be a supplementary analysis of time to the first occurrence of sustained $\geq 50\%$ decline in eGFR, onset of ESKD or death from kidney failure.

The approach to performing this analysis will be identical to the one described in Section 4.2.2.1, where the main analysis of this objective is detailed, with the only difference being a re-definition of the endpoint to include a $\geq 50\%$ decline in eGFR, rather than $\geq 40\%$.

4.2.2.3 Supportive analyses

Time to sustained $\geq 40\%$ (as well as 50%) decline in eGFR, onset of ESKD, and death from kidney failure will be illustrated with Kaplan-Meier plots.

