### 8.1.2 Other Efficacy Assessments

#### Composite Outcome

The components of the composite of kidney failure outcomes are defined below, based on [Levin et al 2020](#):

- Sustained percent decline in eGFR, defined as percent decline in eGFR of  $\geq 40\%$  from the point of randomisation over at least 4 weeks, as evidenced by 2 consecutive central laboratory measurements taken at least 4 weeks apart. The start date of the event is the date of the first central laboratory measurement.
- Onset of ESKD:
  - Kidney transplantation, defined as receipt of a kidney transplant or
  - Maintenance dialysis, defined as dialysis performed for at least 4 weeks, or
  - Sustained low eGFR, defined as eGFR  $< 15 \text{ mL/min}/1.73\text{m}^2$  over at least 4 weeks, as evidenced by 2 consecutive central laboratory measurements taken at least 4 weeks apart.
- Death from kidney failure, defined as the participant dies, AND kidney replacement therapy was never started (irrespective of reason), AND advanced CKD is the underlying cause of death.

The central laboratory will notify the site if there is  $\geq 40\%$  decline in eGFR compared to the point of randomisation or if eGFR is  $< 15 \text{ mL/min}/1.73\text{m}^2$ . A central laboratory re-sampling should be done at an unscheduled visit after at least 4 weeks, and preferably no later than 6 weeks, after the first sampling.

Whether an event of death qualifies as death from kidney failure will be determined by the investigator and indicated in the source documentation and eCRF. Similarly, the initiation of renal replacement therapy (kidney transplantation or maintenance dialysis) will be recorded by the investigator in the source documentation and eCRF.

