3.3 General Considerations

For the purpose of describing the data, summary statistics illustrating the empirical distribution of the variables will be tabulated for most of the collected measurements.

Continuous variables will be summarised using the following descriptive statistics: n (the number of patients included in the analysis), mean, median, standard deviation, minimum, maximum and quartiles where appropriate. Categorical variables will be summarised using number and percentage of observations in each category, with the denominator for the percentages depending on the type and purpose of analyses (e.g., the number of subjects in an analysis set will be used for the tabulations of the baseline characteristics, but number of subjects with available data at a visit will be used for summary statistics by visit tabulations).

In addition, time to event variables will be summarised using Kaplan-Meier estimators of the CDF function. For a selection of continuous variables, in the absence of censoring, the whole eCDF function, rather than a number of different kinds of summary statistics, might be plotted.

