4.2 Endpoint Analyses

This section covers details related to the analyses of primary, secondary, and other endpoints, including sensitivity and supportive analyses.

All the efficacy analyses will be aimed at evaluating the potential effect of SZC during the randomized treatment phase of the study (i.e., the maintenance phase). As such, the estimands for these analyses can be described as follows.

Population: For all of the efficacy analyses specified in the Table 2 below, the population, in estimand terminology, consists of the patients satisfying the randomization criteria of the study. That is, patients who satisfy the inclusion and exclusion criteria at study entry, and who achieve, and maintain, normokalaemia after the initiation and the run-in phases.

Treatment: For all the analyses performed on the maintenance phase, the treatment, in the estimand framework, is SZC and placebo while receiving lisinopril/valsartan, as guided by the CSP. For all the comparisons of SZC vs Placebo, the Placebo group will be used as the reference.

Intercurrent events: The following intercurrent events that might have impact on the interpretation or existence of the measurements associated with the clinical question have been identified:

- Death
- Permanent discontinuation of SZC/Placebo
- Initiation of long-term potassium-lowering treatment

- Introduction of a concomitant medication that may directly affect CKD progression (e.g., SGLT2 inhibitors)
- Onset of ESKD (the definition of which can be found in CSP section 8.1.2 and includes initiation of dialysis or a kidney transplant)
- Change in IP dosage (SZC or RAASi)

It may be hypothesized that a change in IP dosage (SZC or RAASi) may cause an acute haemodynamic effect that, although visible in the eGFR profile, might not reflect a true change in CKD progression but only a temporary change in eGFR. A set of analyses aimed at further evaluating the presence, and potential impact, of such effects will be performed, see Section 4.2.7 for details.

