4.2.2.1 Main analysis

Derivations:

Time to the first occurrence of the components as listed in Table 2, namely sustained $\geq 40\%$ decline in eGFR, onset of ESKD or death from kidney failure, will be derived as the difference between the date of the occurrence and the randomization date, plus one day.

Explicitly, for the different components as listed in CSP Section 8.1.2:

Sustained percent decline in eGFR, is defined as percent decline in eGFR of $\geq 40\%$ from the point of randomisation over at least 4 weeks, as evidenced by 2 consecutive central

laboratory measurements taken at least 4 weeks apart. The start date of the event is the date of the first central laboratory measurement.

Onset of ESKD, is defined as meeting any of the three of the following conditions:

- Kidney transplantation, the date of which is collected directly in the eCRF in a dedicated renal event module.
- Maintenance dialysis, defined as dialysis performed for at least 4 weeks. The date of the start of the dialysis will be used as onset of ESKD date.
- Sustained low eGFR, defined as eGFR < 15 mL/min/1.73 m² over at least 4 weeks, as confirmed by 2 consecutive, non-missing central laboratory measurements < 15 mL/min/1.73 m² taken at least 4 weeks apart. The date of the first such measurement will be used as the date of onset of ESKD.

Death from kidney failure is defined directly by the investigator in the eCRF, as an AE, with the AE date being considered as the date that the event has occurred.

Analysis:

The evaluation of the secondary objective of reducing the incidence of composite outcome of $\geq 40\%$ sustained decline in eGFR, onset of ESKD, and death from kidney failure, will be performed by means of a Cox regression.

The patients will be censored at the end of the maintenance phase, or at the time they leave the study prematurely for any reason (e.g., the date of ICF withdrawal, or the date of last contact in case of a patient lost to follow-up), if such an event occurs. The null hypothesis of no difference between the treatment arms will be tested by considering the hazard ratio (HR) estimate corresponding to treatment. As for other analyses, the estimates of the treatment effect (i.e., hazard ratio between the two treatment arms) alongside the corresponding 95% CI and a p-value, will also be provided.

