Under the same assumptions (i.e., a difference in slopes of 0.75, no acute effect), the power for the chronic slope will be approximately 85%. The evaluation of the chronic slope is assumed to start at 12 weeks.

It is expected that approximately 20% of the eGFR data will be missing. As the eGFR data is correlated within participant, it is assumed that the data points available for a participant will provide information on the missed evaluations, and 20% of missed data would roughly correspond to approximately 10% of randomised participants with no eGFR data available. Hence, 1360 participants will be randomised in the maintenance phase.

Possible Causes for Missing Data during the Randomised Treatment Phase

The initial expectation that approximately 20% of eGFR measurements during the randomised treatment phase will be missing, is largely inferred from DAPA-CKD ([Heerspink et al 2020](#)). Death from any cause and ESKD were identified as the 2 potential main contributors for missing eGFR data. Looking at the placebo group in the aforementioned publication, it is expected that approximately 7% of participants will reach ESKD during the 2 years of randomised treatment phase, and approximately 6% of participants will die. It should be noted that the DAPA-CKD study had a somewhat healthier patient population that included patients with eGFR between 25 and 75 mmol/L (10% of the patient population in the study had an eGFR > 60 mmol/L). In addition, the hyperkalaemia requirement in the STABILIZE-CKD study might lead to a lower baseline eGFR in general, so a somewhat larger percentage of missing data due to the reasons mentioned above is expected. Tentatively, the expectation is that approximately 15% of the missing values will originate from ESKD or death.

In addition to these 2 major reasons, it is expected that data points will also be missing due to a number of smaller issues, such as participants not attending visits, blood samples not being analysable, and participants discontinuing the study, or discontinuing treatment and choosing an alternative follow-up option that precludes blood sampling. The magnitude of such smaller issues is difficult to predict, but it is tentatively expected that they might, cumulatively, lead to an additional 5% of the data points being missing, which would, together with ESKD and death, add up to approximately 20% of missing data.

Signature Page for VV-RIM-06297330 v1.0

Approve: Document Level Task
Verdict: Approved

PPD

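### Kaplan-Meier plots of the kidney composite, with other deaths censored, modestly overstate the cumulative incidence in each arm

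*SAP*

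**What the plan says.** SAP 4.2.2.3 plans one supportive display for Secondary objective #1: time to a sustained 40% (as well as 50%) "decline in eGFR, onset of ESKD, and death from kidney failure will be illustrated with Kaplan-Meier plots". SAP 3.3 sets the general rule that "time to event variables will be summarised using Kaplan-Meier estimators of the CDF function".

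Deaths enter the composite narrowly. Protocol 8.1.2 counts a death only if kidney replacement therapy was never started "AND advanced CKD is the underlying cause of death". The SAP leaves that classification to the site: "Death from kidney failure is defined directly by the investigator in the eCRF" (4.2.2.1).

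On censoring, SAP 4.2.2.1 says: "The patients will be censored at the end of the maintenance phase, or at the time they leave the study prematurely for any reason". Its two examples are consent withdrawal and loss to follow-up; death is not named.

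SAP 4.2 introduces its list of intercurrent events with "The following intercurrent events that might have impact on the interpretation or existence of the measurements associated with the clinical question have been identified", and death comes first in that list. No strategy specific to death follows. Onset of ESKD is the only named exception to treatment policy. Neither document plans a cumulative incidence function, a competing-risk analysis or a version of the composite that counts all deaths.

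SAP 7.3, on expected missing data, says that "approximately 6% of participants will die" over two years and that about 7% will reach ESKD.

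**The concern.** A participant who dies of a cause other than kidney failure can no longer reach the composite. Kaplan-Meier handles that participant like any other censored person, as if the event could still occur later. One minus Kaplan-Meier then describes a setting in which nobody dies of other causes. It is not the distribution function that SAP 3.3 names.

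Within SAP 4.2.2 the planned outputs are a hazard ratio with its confidence interval and p-value, and these plots. The plots are therefore the only planned by-arm display of absolute composite risk, and readers will take risks and risk differences from them. The objective is worded in terms of reducing incidence, which is the quantity that the curves do not quite estimate.

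**Working it through.** **Are other deaths censored?** They are not composite events under Protocol 8.1.2. SAP 4.1.1.1 lists death among the disposition statuses, so a participant who dies has left the study, and the rule covers leaving for any reason. SAP 3.3.1.3 also ends the maintenance phase at last contact. Both parts of the censoring rule lead to censoring, although the SAP does not say so outright.

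**Direction.** At each event time the Kaplan-Meier increment is the composite hazard times the probability of being free of the composite, with other deaths removed. The Aalen-Johansen increment is the same hazard times the probability of being alive and free of the composite. The second probability is never larger. One minus Kaplan-Meier therefore cannot fall below the cumulative incidence, and it exceeds it once a competing death precedes a later event.

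**Inputs.**
- Composite risk: the documents give no event rate, event count or power for the composite, so there is no plan figure to reproduce. I assume 7% to 30% at two years. The 7% is the plan's ESKD expectation (SAP 7.3), a floor because ESKD is one component.
- Competing mortality: about 6% over two years, from any cause (Protocol 9.2, SAP 7.3). I also show an assumed range of 3% to 8%.
- Horizon: two years as planned, and week 69, which is 69/52.18 = 1.32 years.

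**Formulas**, with constant, independent hazards, two-year Kaplan-Meier risk K and two-year death risk D:
- h1 = -ln(1-K)/2 and h2 = -ln(1-D)/2
- 1-KM(T) = 1 - exp(-h1 T)
- CIF(T) = h1/(h1+h2) × [1 - exp(-(h1+h2)T)]

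**Worked case, K = 20%, D = 6%, two years.** h1 = 0.1116 and h2 = 0.0309. The bracket is 1 - 0.80 × 0.94 = 0.248. CIF = 0.1116/0.1425 × 0.248 = 0.194.

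| 1-KM at 2 years | CIF with D = 6% | Overstatement (points) | Relative |
|---|---|---|---|
| 7% | 6.79% | 0.21 | 3.1% |
| 10% | 9.70% | 0.30 | 3.1% |
| 15% | 14.56% | 0.44 | 3.0% |
| 20% | 19.42% | 0.58 | 3.0% |
| 30% | 29.14% | 0.86 | 2.9% |

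A simulation of 2 million participants at K = 15% gave 14.58%, in agreement. With D from 3% to 8% the overstatement runs from 0.10 to 1.15 points.

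A harsher reading takes 6% as the share who actually die free of the composite. A true incidence of 7% to 30% is then overstated by 0.22 to 1.06 points.

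**Week 69.** With the same hazards and D = 6%, the K = 20% case gives 13.72% against 13.45%, or 0.27 points. Over D of 3% to 8% and K of 7% to 30%, the range is 0.05 to 0.55 points.

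**Arm difference.** With K = 15% in one arm, an assumed hazard ratio of 0.75 and equal mortality, the two-year difference is 3.52 points by Kaplan-Meier and 3.42 points by cumulative incidence.

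**The case against.** The strongest reply is that this is too small to matter. At the planned 680 per arm (1360/2), a 15% estimate has a 95% interval of about ±1.96 × √(0.15 × 0.85/680) = ±2.7 points, against a bias of 0.44. The study stopped early, and the SAP describes laboratory measurements beyond week 69 as few. The composite is not itself cut at week 69, but little follow-up lies beyond it. The plots are supportive and illustrative, and no test uses them. Kaplan-Meier with other deaths censored is also the natural companion to the cause-specific hazard that the Cox model estimates. All of this stands. It limits the priority of the point and argues against simply removing the Kaplan-Meier curves. It does not make them an estimate of the distribution function.

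A reader might infer more than the documents support:
- **That 6% is the other-cause death rate.** It is all-cause. Kidney-failure deaths are events, and deaths after a first composite event do not compete. Protocol 9.2 itself expects overlap between ESKD and death. The plan also expects a sicker population than its reference trial, so the true competing rate could lie on either side of 6%.
- **That competing death nearly matches the event rate, because 6% is close to 7%.** The 7% is ESKD alone; the composite also counts sustained eGFR decline.
- **That the bias distorts the treatment comparison.** Unequal bias would need mortality to differ between arms, and the documents give no reason to expect a difference large enough to matter.
- **That the hazard ratio or p-value is wrong.** Censoring these deaths gives a valid cause-specific hazard ratio.

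**Conclusion.** The point holds as a modest presentation error with a certain direction. As planned, the curves overstate the cumulative incidence of both composites in each arm. With the plan's 6% all-cause mortality treated entirely as a competing hazard, the overstatement at two years is about 3% relative and under 1 point (1.06 points at most on the harsher reading). At week 69 it is roughly 0.05 to 0.55 points.

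These sizes rest on constant, independent hazards and on composite risks that I assumed. The direction rests on neither, only on other-cause deaths being censored, which is the natural reading of SAP 4.2.2.1 but is not spelled out there. Secondary objective #1's test and its place in the testing sequence are untouched. The priority is low.

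**What to change.** - **SAP 4.2.2.3:** present Aalen-Johansen cumulative incidence curves by arm for the 40% and 50% composites, with death not from kidney failure as the competing event, as the display of absolute risk. Kaplan-Meier plots may stay alongside, labelled as the companion to the cause-specific Cox model.
- **SAP 4.2.2.1:** state that deaths not from kidney failure are censored at the date of death in the Cox model.
- **SAP 3.3:** qualify the description of Kaplan-Meier as estimating the distribution function for endpoints with a competing death. The same sentence covers time to first lisinopril/valsartan dose decrease (SAP 4.2.3), where every death competes.

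The cost is one added or changed figure per composite, from data already collected and with standard software, plus a few words in three SAP sections. No hazard ratio, p-value or testing order changes.

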4.2.3 Analysis of Secondary objective #2

Secondary objective #2: To determine if treatment with SZC, as adjunct to ACEi/ARB therapy (lisinopril or valsartan), is superior to placebo in reducing the incidence of lisinopril/valsartan dose decrease, in participants on lisinopril/valsartan at randomisation.

Patients not on RAASi at randomization will be excluded from this analysis.

Time to dose reduction used in the model will be derived as the difference between the date of the first instance of RAASi dose decrease post-randomization and the randomization date, plus one day.

The analysis of this objective will be performed by means of a Cox regression, as described in Section 4.2.2.1.

